6.1.6 Dabrafenib-Trametinib Dose Modification for Hemorrhages

Table 6-4: Dabrafenib or Dabrafenib-Trametinib Treatment Modifications for Hemorrhage

Grade 3	
• Hold dabrafenib or dabrafenib-trametinib for up to 3 weeks• If improved, resume the drugs at one dose reduction• If no improvement, permanently discontinue dabrafenib or dabrafenib-trametinib
Grade 4	
• Permanently discontinue dabrafenib or dabrafenib-trametinib

6.1.7 Dabrafenib or Dabrafenib-Trametinib Dose Modification for Pancreatitis

In the event of abdominal pain or suspected pancreatitis, amylase and lipase laboratory samples should be collected for confirmation of the diagnosis. Upon confirmed diagnosis of pancreatitis, dabrafenib should be interrupted until completely resolved. Patients should be closely monitored when re-starting dabrafenib after an episode of pancreatitis.

6.1.8 Dabrafenib or Dabrafenib-Trametinib Dose Modification for Hyperglycemia

Hyperglycemia requiring an increase in the dose of, or initiation of insulin or oral therapy can occur with dabrafenib. Monitor serum glucose levels as clinically appropriate during treatment with dabrafenib in subjects with pre-existing diabetes or hyperglycemia. Advise patients to report symptoms of severe hyperglycemia such as excessive thirst or any increase in the volume or frequency of urination.

6.1.9 Dabrafenib + Trametinib Dose Modification for Renal Insufficiency

Cases of renal insufficiency have occurred in patients receiving the combination of dabrafenib and trametinib. Prior to start of study treatment, concomitant medications should be reviewed for the potential risk of inducing nephrotoxicity and modified if clinically possible.

Table 6-5: Dabrafenib or Dabrafenib + Trametinib Dose Modification for Renal Insufficiency

Serum Creatinine Level	Management Guideline	Action and Dose Modification

Serum creatinine increase >0.2 mg/dL (18 mcmol/L)
 
BUT
 
≤0.5 mg/dL (44 mcmol/L) above baseline
	
• Recheck serum creatinine within 1 week.• If elevation persists beyond 4 weeks, recommend evaluation (consider renal biopsy) for etiology; consider nephrology consultation.• If pyrexia is present, treat pyrexia as per guidelines.^a	Continue study treatment at the same dose level.

Table 6-5: Dabrafenib or Dabrafenib + Trametinib Dose Modification for Renal Insufficiency

Serum Creatinine Level	Management Guideline	Action and Dose Modification
Serum creatinine increase >0.5 mg/dL (44 μmol/L)	
Monitor serum creatinine ≥2-times per week.Hospitalization may be necessary if serum creatinine cannot be monitored frequently.If pyrexia is present, treat pyrexia per guidelines.^aConsult nephrologist if clinically indicated.Perform renal biopsy if clinically indicated, for example:
Renal insufficiency persists despite volume repletion.Patient has new rash or signs of hypersensitivity (such as elevated eosinophil count).	
Interrupt study treatment until serum creatinine recovers to baseline.Restart study treatment.^b

^a NSAIDs can induce renal insufficiency, especially in patients with dehydration; encourage oral fluids or consider IV fluids as clinically indicated. See guidelines for pyrexia Section 6.1.2.

^b Investigator may restart at either the same or a reduced dose level. Escalation of study treatment to previous dose level is allowed if another episode of renal insufficiency does not occur after 4 weeks of dose reduction.

6.1.10 Dabrafenib + Trametinib Dose Modification for **Reduced Left Ventricular Ejection Fraction**

Decreases of the left ventricular ejection fraction (LVEF) have been observed in patients receiving dabrafenib plus trametinib.

Table 6-6: Dabrafenib + Trametinib Treatment Modification and Management Requirements for LVEF Decrease

Clinic	LVEF-drop (%) or CTCAE grade	Dose Modification
Symptomatic^a	
• Grade 3: resting LVEF 39-20% or >20% absolute reduction from baseline• Grade 4: Resting LVEF $\leq 20\%$.	
• Permanently discontinue trametinib. Report as SAE• Hold dabrafenib until LVEF improves.• Consult with cardiologist.• Repeat ECHO after 2, 4, 8, 12, and 16 weeks or until resolution.

^a If ECHO does not show LVEF recovery within 2 weeks, repeat ECHO 2 weeks later (prior to reaching end of 4 weeks).

^b Symptoms may include: dyspnea, orthopnea, and other signs and symptoms of pulmonary congestion and edema.

6.1.11 Dabrafenib or Dabrafenib + Trametinib Dose Modification for **Hypertension**

Increases in blood pressure (BP) have been observed in patients receiving dabrafenib plus trametinib. Requirements for BP monitoring and management are provided below.

- **Persistent hypertension** is defined as an increase of systolic BP (SBP) >140 mmHg and/or diastolic BP (DBP) >90 mmHg in three consecutive visits with blood pressure assessments from two readings collected as described above.
- **Asymptomatic hypertension** is defined as an increase of SBP >140 mmHg and/or diastolic BP (DBP) >90 mmHg in the absence of headache, light-headedness, vertigo, tinnitus, episodes of fainting, or other symptoms indicative of hypertension.
- **Symptomatic hypertension** is defined as hypertension aggravated by symptoms (e.g., headache, light-headedness, vertigo, tinnitus, episodes of fainting) that resolve after the blood pressure is controlled within the normal range

Table 6-7: Dabrafenib or Dabrafenib + Trametinib Treatment Modification and Management Requirements for Hypertension

Event	Management Guideline	Dose Modification
(Scenario A) Asymptomatic and persistent ^a SBP of ≥ 140 and < 160 mmHg, or DBP ≥ 90 and < 100 mmHg OR clinically significant increase in DBP of 20 mmHg (but still below 100 mmHg)	
 • Adjust current or initiate new antihypertensive medication(s). • Titrate antihypertensive medication(s) during the next 2 weeks to achieve well-controlled^b BP. • If BP is not well-controlled within 2 weeks, consider referral to a specialist and go to scenario (B). 	
 • Continue protocol therapy.
(Scenario B) Asymptomatic SBP ≥ 160 mmHg, or DBP ≥ 100 mmHg OR Failure to achieve well-controlled BP within 2 weeks in Scenario A.	
 • Adjust current or initiate new antihypertensive medication(s). • Titrate antihypertensive medication(s) during the next 2 weeks to achieve well-controlled BP. 	
 • Interrupt study treatment if clinically indicated. • Once BP is well-controlled^b, restart study treatment reduced by one dose level.
(Scenario C) Symptomatic hypertension OR Persistent SBP ≥ 160 mmHg, or DBP ≥ 100 mmHg, despite antihypertensive medication and dose reduction of study treatment	
 • Adjust current or initiate new antihypertensive medication(s). • Titrate antihypertensive medication(s) during the next 2 weeks to achieve well-controlled BP. • Referral to a specialist for further evaluation and follow-up is recommended. 	
 • Interrupt study treatment if clinically indicated. • Once BP is well controlled, restart study treatment reduced by one dose level.^c
(Scenario D) Refractory hypertension unresponsive to above interventions or hypertensive crisis.	
 • Continue follow-up per protocol. 	
 • Permanently discontinue study treatment.

a. Hypertension detected in two separate readings during up to three consecutive visits
 
b. Well-controlled blood pressure defined as SBP ≤ 140 mm Hg and DBP ≤ 90 mm Hg in two separate readings during up to three consecutive visits.
 
c. Escalation of trametinib to previous dose level can be considered if BPs remain well-controlled for 4 weeks after restarting of trametinib.
 
d. Symptomatic hypertension defined as hypertension aggravated by symptoms (e.g., headache, light-headedness, vertigo, tinnitus, episodes of fainting) that resolve after the blood pressure is controlled within the normal range
		

6.1.12 Dabrafenib or Dabrafenib + Trametinib Dose Modification for **QTc Prolongation**

Table 6-8: Dabrafenib + Trametinib modification for QTc Prolongation

Prolongation	Action and Dose Modification
• QTcB \geq 501 msec ^a	
Interrupt study treatment until QTcB prolongation resolves to grade 1 or baseline.Test serum potassium, calcium, phosphorus and magnesium. If abnormal, correct per routine clinical practice to within normal limits.Review concomitant medication usage for agents that prolonged QTc.If the event resolves, restart study treatment at current dose level.^bIf the event does not resolve, permanently discontinue study treatment. Consider evaluation with cardiologist.If the event recurs, permanently discontinue study treatment. Consider evaluation with cardiologist.

Abbreviations: msec = milliseconds; QTcB = QT interval on electrocardiogram corrected using the Bazett's formula

a. Based on average QTc value of triplicate ECGs. For example, if an ECG demonstrates a prolonged QT interval, obtain two or more ECGs over a brief period, and then use the averaged QTc values of the three ECGs to determine if study treatments should be interrupted or discontinued.

b. If the QTc prolongation resolves to grade 1 or baseline, the subject may resume study treatment.

6.1.13 Dabrafenib or Dabrafenib + Trametinib Dose Modification for **Diarrhea**

Episodes of diarrhea have been observed in patients receiving dabrafenib, trametinib, or both therapies in combination. Other, frequent causes for diarrhea including concomitant medications (e.g., stool softeners, laxatives, antacids, etc.), infections caused by *C. difficile* or other pathogens, partial bowel obstruction, etc., should be clinically excluded.

Table 6-9: Dabrafenib or Dabrafenib + Trametinib Treatment Modification and Management Recommendations for Diarrhea Suspected to be Related to Treatment

CTCAE Grade	Management Recommendations	Action and Dose Modification
Uncomplicated Diarrhea,¹ Grade 1 or 2 (tolerable)	
 Diet: Stop all lactose containing products; eat small meals, BRAT-diet (banana, rice, apples, toast) recommended. Hydration: 8-10 large glasses of clear liquids per day (e.g., Gatorade or broth). Loperamide³: Initially 4 mg, followed by 2 mg every 4 hours or after every unformed stool; maximum 16 mg/day. Continue until diarrhea-free for 12 hours. Diarrhea >24 hours: Loperamide 2 mg every 2 hours; maximum 16 mg/day. Consider adding oral antibiotics. Diarrhea >48 hours: Loperamide 2 mg every 2 hours; maximum 16 mg/day. Add budesonide or other second-line therapies (otreotide, or tincture of opium) and oral antibiotics. 	
 Continue study treatment. If diarrhea is grade 2 for > 48 hours, interrupt study treatment until diarrhea resolves to grade ≤ 1. Restart study treatment at the same dose level.
Uncomplicated Diarrhea,¹ Grade 2 (intolerable), 3, or 4 Any Complicated Diarrhea²	
 Clinical evaluation mandatory. Loperamide³: Initially 4 mg, followed by 2 mg every 4 hours or after every unformed stool; maximum 16 mg/day. Continue until diarrhea-free for 12 hours. Oral antibiotics and second-line therapies if clinically indicated Hydration: Intravenous fluids if clinically indicated. Antibiotics (oral or intravenous) if clinically indicated. Intervention should be continued until the subject is diarrhea-free for ≥ 24 hours. Intervention may require hospitalization for subjects at risk of life-threatening complications. 	
 Interrupt study treatment until diarrhea resolves to \leq grade 1. Restart with study treatment reduced by one dose level.⁴ If 3 dose reductions of study treatment are clinically indicated, permanently discontinue study treatment.

1. **Uncomplicated diarrhea** defined by the absence of symptoms such as cramping, nausea/vomiting, \geq grade 2, decreased performance status, pyrexia, sepsis, neutropenia \geq grade 3, frank bleeding, and/or dehydration requiring intravenous fluid substitution.

2. **Complicated diarrhea** defined by the presence of symptoms such as cramping, nausea/vomiting, \geq grade 2, decreased performance status, pyrexia, sepsis, neutropenia \geq grade 3, frank bleeding, and/or dehydration requiring intravenous fluid substitution.

3. Loperamide should be made available prior to start of study treatment so loperamide administration can begin at the first signs of diarrhea.

4. Escalation of study treatment to previous dose level is allowed after consultation with the medical monitor and in the absence of another episode of complicated or severe diarrhea in the 4 weeks subsequent to dose reduction.

6.1.14 Dabrafenib or Dabrafenib + Trametinib Dose Modification for Vision Changes Suspected to be Related to Treatment

Episodes of vision changes have been observed in patients receiving dabrafenib, trametinib, or the combination of both therapies. An ophthalmologist should be consulted if changes in vision develop. However, if the visual changes are clearly unrelated to study treatment (e.g., allergic conjunctivitis), then monitor closely as it may be reasonable to defer ophthalmic examination.

Uveitis and iritis have been associated with dabrafenib, while RPED and RVO have been associated with trametinib therapy. Monitor patients for visual signs and symptoms (such as change in vision, photophobia, and eye pain) during therapy. Special attention should be given to retinal findings (e.g., retinal pigment epithelial detachment (RPED) or retinovascular abnormalities (i.e., branch or central retinal vein occlusions [RVO])). For events of visual changes regardless of severity but for which an ophthalmic examination is conducted, a blood sample for PK analysis is encouraged when feasible, and the blood sample should be drawn as close as possible to the time of the event.

The ophthalmology exam will include best corrected visual acuity, visual field examination, tonometry, slit lamp biomicroscopic examination of the anterior segment (with special attention to inflammation) and the posterior segment, and dilated indirect fundoscopy with special attention to retinal abnormalities. Optical coherence tomography is strongly recommended at scheduled visits and if retinal abnormalities are suspected. Other types of ancillary testing including color fundus photography, and fluorescein angiography may also be indicated as determined by clinical exam.

Guidelines regarding event management and dose reduction for visual changes considered to be related to study treatment are provided in the table below.

Table 6-10: Dabrafenib or Dabrafenib-Trametinib Treatment Modification for Visual Changes Considered to be Related to Study Treatment

CTCAE Grade	Management Guideline	Action and Dose Modification
Grade 1	
Consult ophthalmologist immediately.	
If dilated fundus examination cannot be performed within 7 days of onset, hold trametinib until RPED and RVO can be excluded by retina specialist/ ophthalmologist. Dabrafenib may be continued.If RPED and RVO excluded, continue (or restart) trametinib at same dose levelIf Uveitis/Iritis, refer to table below for Iritis/UveitisIf RPED suspected or diagnosed, refer to RPED dose modification table below; report as SAE if diagnosed.If RVO suspected or diagnosed: Permanently discontinue trametinib and report as SAE if diagnosed.

CTCAE Grade	Management Guideline	Action and Dose Modification
Grade 2 and 3	
 Consult ophthalmologist immediately. 	
 Hold trametinib. Dabrafenib may be continued. If RPED and RVO excluded, restart trametinib at same dose level If Uveitis/Iritis, refer to table below for Uveitis/Iritis If RPED diagnosed, see RPED dose modification table below; report as SAE. If RVO diagnosed: Permanently discontinue trametinib and report as SAE.
Grade 4	
 Consult ophthalmologist immediately. 	
 Interrupt trametinib. Dabrafenib may be continued. If RPED and RVO excluded, may consider restarting trametinib at same or reduced dose after discussion with study medical monitor. If Uveitis/Iritis, refer to table below If RVO or RPED diagnosed, permanently discontinue trametinib and report as SAE.

Abbreviations: RPED = retinal pigment epithelial detachments; RVO = retinal vein occlusion; SAE = serious adverse event

*If visual changes are clearly unrelated to study treatment (e.g., allergic conjunctivitis), monitor closely but ophthalmic examination is not required

Table 6-11: Dose Modification for RPED

Event CTCAE Grade	Action and Dose Modification
Grade 1 RPED (Asymptomatic; clinical or diagnostic observations only)	
 Continue trametinib with retinal evaluation monthly until resolution. If RPED worsens, follow instructions below. Dabrafenib treatment is not affected
Grade 2-3 RPED (Symptomatic with mild to moderate decrease in visual acuity; limiting instrumental ADL)	
 Interrupt trametinib. Continue dabrafenib. Retinal evaluation monthly until resolution. If improved to \leq Grade 1, restart trametinib with one dose level reduction (reduced by 0.5 mg) or discontinue in patients taking trametinib 1 mg daily. If no recovery within 4 weeks permanently discontinue trametinib.

Table 6-12: Dabrafenib or Dabrafenib-Trametinib Dose Modification for Uveitis and Iritis

CTCAE Grade	Action and Dose Modification
Uveitis and Iritis	
 Continue study treatment Control ocular inflammation with local therapies If not improved to grade ≤ 1 within 1 week, interrupt dabrafenib until resolution of ocular inflammation and then restart dabrafenib reduced by one dose level If no recover within 4 weeks, permanently discontinue dabrafenib. Trametinib may be continued.

6.1.15 Dabrafenib + Trametinib Dose Modification for Pneumonitis Suspected to be Related to Treatment

Pneumonitis has been observed in patients receiving trametinib in combination with dabrafenib. To reduce the risk of pneumonitis, patients will be monitored closely for symptoms, evaluated with imaging and functional tests when appropriate.

Table 6-13: Dabrafenib-Trametinib Treatment Modification for Pneumonitis Suspected to be Related to Treatment

CTCAE Grade	Adverse Event Management	Action and Dose Modification
Grade 1	
 CT scan (high-resolution with lung windows) recommended. Clinical evaluation and laboratory work-up for infection. Monitoring of oxygenation via pulse-oximetry recommended. Consultation with pulmonologist recommended. 	Continue study treatment at current dose
Grade 2	
 CT scan (high-resolution with lung windows). Clinical evaluation and laboratory work-up for infection. Consult pulmonologist. Pulmonary function tests: If $<$ normal, repeat every 8 weeks until \geq normal. Bronchoscopy with biopsy and/or BAL recommended Symptomatic therapy including corticosteroids if clinically indicated. 	
 Interrupt trametinib until recovery to grade ≤ 1. Restart with trametinib reduced by one dose level. Escalation to previous dose level after 4 weeks If no recovery to grade ≤ 1 within 4 weeks, permanently discontinue trametinib.
Grade 3	
 Same as grade 2 	
 Interrupt study treatment until recovery to grade ≤ 1. Resumption of trametinib at one dose level reduction may be considered If no recovery to grade ≤ 1 within 4 weeks, permanently discontinue trametinib.

CTCAE Grade	Adverse Event Management	Action and Dose Modification
Grade 4	• Same as grade 2	Permanently discontinue trametinib.

6.1.16 Dabrafenib or Dabrafenib + Trametinib Dose Modification for Liver Chemistry Changes

Table 6-14: Dabrafenib or Dabrafenib-Trametinib Dose Modification for Liver Chemistry Changes

Event	Treatment modifications and assessment/monitoring

 • ALT \geq3x ULN but <5x ULN and Total Bilirubin <2x ULN, without symptoms considered related to liver injury or hypersensitivity and who can be monitored weekly for 4 weeks 	
 • May continue study treatment. • If liver chemistry stopping criteria are met any time, proceed as described below. 
MONITORING: Repeat ALT, AST, ALK, and total bilirubin until they return to normal/baseline or stabilise


Criteria for discontinuing study drug: When any of the liver stopping criteria below is met, discontinue trametinib and dabrafenib
 
 1. ALT \geq3xULN and Total bilirubin \geq2x ULN or $>35\%$ direct bilirubin^{1,2} 2. ALT \geq 3xULN and INR >1.5, if INR measured and if subject is not on anticoagulation² 3. ALT \geq5x ULN 4. ALT \geq3x ULN persists for ≥ 4 weeks 5. ALT \geq3x ULN and cannot be monitored weekly for 4 weeks 6. ALT \geq3x ULN associated with symptoms³ (new or worsening) believed to be related to liver injury or hypersensitivity 	
 • Immediately discontinue study treatment. • Do not restart/rechallenge • Perform liver event ASSESSMENT AND WORKUP (see below). • Monitor the subject until liver chemistries resolve, stabilize, or return to baseline (see MONITORING below). If applicable, provide details on required follow up assessments (e.g., follow up for overall survival or disease recurrence or progression). 
MONITORING: In patients stopping for criteria 1-2 (with abnormal TB and INR, indicating potentially more significant liver toxicities):
 
 • Repeat ALT, AST, ALK, and total bilirubin) and perform liver assessment and workup within 24 hours. • Monitor subjects twice weekly until LFT return to normal/baseline or stabilize. • A specialist or hepatology consultation is recommended. 
In patients stopping for criteria 2-6:
 
 • Repeat LFT and perform liver event follow up assessments within 24-72 hours • Monitor subjects weekly until LFTs return to normal/baseline or stabilize. 
ASSESSMENT and WORKUP:
 
 • Viral hepatitis serology.⁴ • If possible, obtain blood sample for PK analysis.⁵ • Serum CPK and LDH. • Fractionate bilirubin, if total bilirubin \geq2x ULN.

Event	Treatment modifications and assessment/monitoring
	
 • CBC with differential to assess eosinophilia. • Record clinical symptoms of liver injury, or hypersensitivity on AE CRF. • Record concomitant medications (including acetaminophen, herbal remedies, other over the counter medications). • Record alcohol use. 
Additional work up for patient stopping for criteria 1-2 (with abnormal TB and INR, indicating potentially more significant liver toxicities):
 
 • Anti-nuclear antibody, anti-smooth muscle antibody, Type 1 anti-liver kidney microsomal antibodies, and quantitative total immunoglobulin G (IgG or gamma globulins). • Serum acetaminophen adduct HPLC assay (in subjects with likely acetaminophen use in the preceding). • If there is underlying chronic hepatitis B (e.g. positive hepatitis B surface antigen): quantitative hepatitis B DNA and hepatitis delta antibody.⁶ • Liver imaging (ultrasound, MRI, CT) and /or liver biopsy.

Footnotes

1. Serum bilirubin fractionation should be performed if testing is available. If serum bilirubin fractionation testing is unavailable, record presence of detectable urinary bilirubin on dipstick, which indicates direct bilirubin elevations and suggesting liver injury.
2. All events of ALT $\geq 3 \times$ ULN and bilirubin $\geq 2 \times$ ULN ($>35\%$ direct bilirubin) or ALT $3 \times$ ULN and INR >1.5 (if INR measured) may indicate severe liver injury (possible “Hy’s Law”). INR measurement is not required, and the threshold value stated will not apply to subjects receiving anticoagulants.
3. New or worsening symptoms believed to be related to liver injury (such as fatigue, nausea, vomiting, right upper quadrant pain or tenderness, or jaundice) or believed to be related to hypersensitivity (such as fever, rash or eosinophilia)
4. Includes: Hepatitis A IgM antibody; Hepatitis B surface antigen and Hepatitis B Core Antibody (IgM); Hepatitis C RNA; Cytomegalovirus IgM antibody; Epstein-Barr viral capsid antigen IgM antibody (or if unavailable, obtain heterophile antibody or monospot testing); Hepatitis E IgM antibody
5. PK sample is desired if feasible. Record the date/time of the PK blood sample draw and the date/time of the last dose of study treatment prior to blood sample draw on the CRF. If the date or time of the last dose is unclear, provide the subject’s best approximation. If the date/time of the last dose cannot be approximated OR a PK sample cannot be collected in the time period indicated above, do not obtain a PK sample. Not required for single-dose studies.
6. If hepatitis delta antibody assay cannot be performed, it can be replaced with a PCR of hepatitis D RNA virus (where needed) (Le Gal *et al.*, 2005).

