3.1.5 Age ≥ 18 years. Because no dosing or adverse event data are currently available on the use of INCB039110 in combination with dabrafenib and trametinib in patients < 18 years of age, children are excluded from this study, but will be eligible for future pediatric trials.

3.1.6 ECOG performance status ≤ 1 (Karnofsky $\geq 70\%$, see Appendix A).

3.1.7 Life expectancy of greater than 3 months in the opinion of the investigator.

3.1.8 Patients must have acceptable organ and marrow function as defined below:

– Leukocytes (WBCs)	$\geq 3,000/\mu\text{L}$
– absolute neutrophil count	$\geq 1,500/\mu\text{L}$
– hemoglobin	$\geq 9 \text{ g/dL}$ (patients may be transfused to this level)
– platelets	$\geq 100,000/\mu\text{L}$
– total bilirubin	$< 1.5 \times$ institutional upper limit of normal

OR

- AST(SGOT)/ALT(SGPT)	> 1.5 x institutional upper limit of normal allowed if direct bilirubin is within normal range.
- PT/INR and PTT	$\leq 2.5 \times$ institutional upper limit of normal
- Serum creatinine	$< 1.3 \times$ ULN ¹ $\leq 1.5 \text{ mg/dL}$ OR creatinine clearance $\geq 50 \text{ mL/min/1.73 m}^2$
- Potassium	$> 3 \text{ and } < 5.5 \text{ mmol/L}$
- Magnesium	$> 1.2 \text{ and } < 2.5 \text{ mg/dL}$

¹Therapeutic levels of anti-coagulation are permitted if clinically indicated, as per section 3.2.15. Thus PT/INR may be >1.3 if therapeutically anti-coagulated.

3.1.9 The effects of INCB039110, dabrafenib, and trametinib on the developing human fetus are unknown. For this reason, women of child-bearing potential must have a *negative serum pregnancy test within 14 days prior to registration and agree to use effective contraception* (barrier method of birth control, or abstinence; hormonal contraception is not allowed due to drug-drug interactions which can render hormonal contraceptives ineffective) *from 14 days prior to registration*, throughout the treatment period, and for 4 months after the last dose of study treatment. Should a woman become pregnant or suspect she is pregnant while she is participating in this study, she should inform her treating physician immediately.

Based on studies in animals, it is also known that dabrafenib may cause damage to the tissue that makes sperm. This may cause sperm to be abnormal in shape and size and could lead to infertility, which may be irreversible.

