5.1 Pre-Treatment Criteria

5.1.1 Screening Visit: Patients must meet criteria at screening as outlined in Section 3.1.

- Of note, screening eligibility labs do not need to be repeated on cycle 1 day 1. If labs are drawn on Cycle 1, Day 1 will not be used to reconfirm eligibility. Eligibility is confirmed at screening; it is not required to be reassessed on Cycle 1, Day 1. Please see section 5.1.2 and the study calendar (Section 10) for information on laboratory studies and treatment parameters.

5.1.2 Hematologic Parameters for treatment:

Absolute Neutrophil Count

- Cycle 1, Day 1: $\geq 1,500/\mu\text{L}$
- Cycle 2 and Beyond, Day 1: Per Table in Section 6.2.1.1

White Blood Cell Count

- Cycle 1, Day 1: $\geq 3,000/\mu\text{L}$
- Cycle 2 and Beyond, Day 1: Per Table in Section 6.2.1.1

Hemoglobin

- Cycle 1, Day 1: $\geq 9\text{ g d/gl}$ (patients may be transfused to this level)
- Cycle 2 and Beyond, Day 1: Per Table in Section 6.2.1.1

Platelets

- Cycle 1, Day 1: $\geq 100,000/\mu\text{L}$
- Cycle 2 and Beyond, Day 1: Per Table in Section 6.2.1.1

5.1.3 Liver Function Parameters for treatment:

Transaminases (AST/ALT):

- Cycle 1, Day 1: $\leq 2.5 \times$ institutional upper limit of normal
- Cycle 2 and Beyond, Day 1: Per Table in Section 6.1.16

Bilirubin

- Cycle 1, Day 1: $< 1.5 \times$ institutional upper limit of normal
OR
 $> 1.5 \times$ institutional upper limit of normal allowed if direct bilirubin is within normal range
- Cycle 2 and Beyond, Day 1: Per Table in Section 6.1.16

5.1.4 Renal Function Parameters for treatment:

Creatinine:

- Cycle 1, Day 1: $\leq 1.5 \text{ mg/mL}$ OR creatinine clearance $\geq 50 \text{ mL/min}/1.73 \text{ m}^2$
- Cycle 2 and Beyond, Day 1: Per Table in Section 6.1.9

5.1.5 All Cycles, Day 1: Patients must have all the following:

- Adequate blood pressure control as detailed in Section 6.1.11.
- ECOG performance status of 0 or 1.
- No evidence of life-threatening medical problems.

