5.5 Duration of Therapy

In the absence of treatment delays due to adverse event(s), treatment may continue until one of the following criteria applies:

- Disease progression,
- Intercurrent illness that prevents further administration of treatment,
- Unacceptable adverse event(s),
- Patient decides to withdraw from the study, or
- General or specific changes in the patient's condition render the patient unacceptable for further treatment in the judgment of the investigator.

Participants will be removed from the protocol therapy when any of these criteria apply. The reason for removal from protocol therapy, and the date the participant was removed, must be documented in the case report form (CRF). Alternative care options will be discussed with the participant.

In the event of unusual or life-threatening complications, treating investigators must immediately (within 24 hours of awareness of the event) notify the Overall PI, [name]., P.h.D at [contact], [name].

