5.6 Duration of Follow Up

Participants will be followed for 2 years after removal from study treatment or until death, whichever occurs first. Participants removed from study treatment for unacceptable adverse events will be followed until resolution or stabilization of the adverse event. All patients will have a follow-up encounter 30 days (+ 3 days) after last study treatment for assessment of adverse effects. This encounter can be carried out in clinic or over the telephone. Following discontinuation of dabrafenib, monitoring for non-cutaneous secondary/recurrent malignancies should continue for up to 6 months or until initiation of another anti-neoplastic therapy. Dermatologic skin assessments should be completed every 3 months for 6 months after discontinuation of dabrafenib or initiation of another anti-neoplastic therapy. Participants' vital status will be followed every 6 months (telephone contact is adequate) following removal from the study treatment. Date and cause of death should be provided for participants who become deceased within the 2-year interval following removal from the study treatment.

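### Table 6-14's liver stopping row does not say whether INCB039110 stops, so the plan permits it to continue or restart after a possible Hy's Law event; criterion 2 also has two monitoring schedules

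*Combined protocol and SAP*

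**What the plan says.** Section 6.1.16 deals with liver chemistry. Its table is headed "Table 6-14: Dabrafenib or Dabrafenib-Trametinib Dose Modification for Liver Chemistry Changes", and the section title has the same two-drug scope. In the stopping row, the cell listing the six criteria says "When any of the liver stopping criteria below is met, discontinue trametinib and dabrafenib". The action cell says "Immediately discontinue study treatment" and forbids rechallenge. Footnote 2, attached to criteria 1 and 2 (raised ALT with raised bilirubin, or with raised INR), describes such events as possible Hy's Law.

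The action cell then sets monitoring. Criteria 1–2 get repeat tests and work-up within 24 hours, then twice-weekly follow-up. A second heading, for criteria 2–6, gives 24–72 hours and then weekly.

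Other sections bear on INCB039110:

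- Sections 5.2.3 and 6.2 let it continue, at the investigator's discretion, if dabrafenib, trametinib or both are stopped for toxicity.
- The opening of Section 6 asks for the responsible drug to be identified and, where that is difficult, applies each drug's own modification rules.
- Section 6.2.1 introduces Table 6-15, the INCB039110 table, for severe falls in neutrophils, hemoglobin or platelets.
- Section 5.1.3 sends AST/ALT and bilirubin from the second cycle onward to the liver table: "Cycle 2 and Beyond, Day 1: Per Table in Section 6.1.16".
- Section 5.5 lists reasons to stop therapy, including unacceptable adverse events: "Participants will be removed from the protocol therapy when any of these criteria apply".

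**The concern.** This is a mandatory stopping rule for events that the protocol itself says may reflect severe liver injury. Two careful sites could follow it differently. One would stop all three drugs permanently. The other would stop dabrafenib and trametinib, then decide case by case whether to go on with INCB039110. The drug left to discretion is the investigational one, and Section 2.5.1 notes that the pharmacokinetics of the triple combination have not been studied.

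The overlap in monitoring has the same character. A patient with ALT and INR both raised could properly be put on the slower schedule. What is at stake is patient safety and uniform conduct across sites, not the analysis.

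**Working it through.** No plan figure needs reproducing. The check is a comparison of texts, followed by a small illustration of scale.

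**1. What is certain.** On any reading, dabrafenib and trametinib stop. The open question is INCB039110 alone.

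**2. What *study treatment* means.** The text gives no definition, and usage shifts:

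- Section 3.1.9 opens with all three drugs and requires contraception "for 4 months after the last dose of study treatment". Here it is the whole regimen.
- Section 5.6 says "Participants will be followed for 2 years after removal from study treatment or until death, whichever occurs first". Again it is the whole regimen.
- In Table 6-15 it is INCB039110.
- In the Section 6.1 tables it appears under titles that name only dabrafenib and trametinib.

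**3. The two readings.**

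- *Three-drug reading:* the action cell governs. INCB039110 stops at once and is not rechallenged.
- *Doublet reading:* the titles and the criteria cell govern, and *study treatment* refers back to them. The table is then silent on INCB039110, and Sections 5.2.3 and 6.2 permit it to continue.

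**4. Does anything else settle it?**

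- *Opening of Section 6.* Unclear attribution goes to each drug's own rules, but INCB039110 has no liver-specific rule.
- *Table 6-15.* Its lead-in concerns three blood counts. If it were applied to liver events because its title refers to toxicities generally, a Grade 3 or first Grade 4 event would mean interruption and then restart one dose level lower after recovery. That differs from both readings in step 3.
- *Section 5.1.3.* Sending liver tests to 6.1.16 without limiting this to the doublet suggests that the table governs the regimen. The table still does not name INCB039110.
- *Sections 5.5 and 5.1.5.* Removal for an unacceptable event, and the requirement of no life-threatening problem on Day 1 of each cycle, are judgements. Neither sets a liver threshold.

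None of these closes the gap.

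**5. Monitoring.** Criterion 2 belongs to both ranges, 1–2 and 2–6. The additional work-up in the same table again groups it with criterion 1, so the second heading looks like a slip for 3–6.

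**6. Scale.** The documents give no rate for criteria 1–2, for the doublet or the triplet. The nearest figures are for dabrafenib plus trametinib 2 mg (Section 2.3.2.4): raised ALT 42% (Grade 3–4, 4%) and hyperbilirubinemia 15% (Grade 3–4, 0%). They are not cross-tabulated, so no joint rate follows. As assumptions only, take a per-patient trigger rate p and the maximum enrollment n = 38 (Section 13.2):

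expected patients = 38p; P(at least one) = 1 − (1 − p)^38

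| assumed p | expected | P(at least one) |
|---|---|---|
| 0.5% | 0.19 | 0.17 |
| 1% | 0.38 | 0.32 |
| 2% | 0.76 | 0.54 |
| 5% | 1.90 | 0.86 |

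These count laboratory triggers, not patients who would actually be kept on INCB039110. The range is too wide to serve as an estimate. It shows only that a single case is plausible in a trial of this size.

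**The case against.** The best reply is that the two cells agree. The titles and the criteria cell name the doublet, and *study treatment* in the next cell refers back to it. Agent-specific handling also has a basis. Section 6.2.1 says that blood-count falls are the only consistent effects of INCB039110, while hepatic events are listed among the MEK-category events of special interest. Investigator discretion is bounded by Section 5.5, which also requires the Overall PI to be told of life-threatening complications within 24 hours, and by Section 5.1.5.

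Much of this stands. It removes the contradiction between the cells, but it leaves the investigational drug with no liver rule and a clause permitting it to continue. INCB039110 is not cleared by the data shown either. In its myelofibrosis study (Section 2.2.4) ALT was raised in 5 of 87 patients, AST in 6 of 87 and blood bilirubin in 5 of 87. That table has no control group, so it does not show causation.

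A reader might infer that the protocol commands opposite actions, or keeps such patients on INCB039110. It does not: continuation is permitted, never required. Nor do the documents show that Table 6-15 governs liver events, since its lead-in is about blood counts. The unstudied triplet pharmacokinetics should not be pressed into a predicted interaction: Section 2.5.1 sees little risk of altered dabrafenib or trametinib clearance, and Section 9.2 considers an interaction unlikely.

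**Conclusion.** The point holds as a gap in a safety rule. Table 6-14 stops dabrafenib and trametinib and does not settle INCB039110, so the plan as written permits a patient with a possible Hy's Law event to stay on, or restart, the investigational drug. The duplicate schedule for criterion 2 is plain on the page.

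Confidence is high on the missing definition, the absence of a liver threshold naming INCB039110, and the monitoring overlap. Which reading sites would adopt is not known, nor is the frequency of triggers on the triplet. The absence of Hy's Law cases reported for the doublet study in Section 2.3.2.4 does not bound it: Section 2.3.1 says trametinib liver abnormalities were often confounded by other conditions, other drugs and liver metastases, and the criteria in the row are laboratory triggers. No endpoint, estimate or sample size is affected. It should be corrected because the repair is cheap and the event, though perhaps rare, is serious.

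**What to change.** Change wording in four places:

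1. In the stopping row of Table 6-14, state that for criteria 1–2 dabrafenib, trametinib and INCB039110 are all permanently discontinued and not rechallenged.
2. In the same row, state what happens to INCB039110 for criteria 3–6, and replace *study treatment* with the named drugs. The same ambiguity applies to those criteria, so fixing only 1–2 would leave it in place.
3. Make the continuation clauses in Sections 5.2.3 and 6.2, and any restart under Table 6-15, subject to that row.
4. Change the second monitoring heading from criteria 2–6 to criteria 3–6, so that criterion 2 has only the 24-hour, twice-weekly schedule.

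The cost is protocol wording, with no added procedures. The downside is that an occasional patient loses INCB039110 when it was not the cause. How often is unknown. On the assumed 0.5% to 5% range it would be at most 0.19 to 1.9 of 38 patients for criteria 1–2, and only if every trigger had another cause.
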